2.1.2 Exclusion Criteria

2.1.2.1 Clinically significant systemic illness (e.g. serious active infections or significant cardiac, pulmonary, hepatic or other organ dysfunction), that in the judgment of the PI would compromise the patient's ability to tolerate protocol therapy or significantly increase the risk of complications.

2.1.2.2 Patients with a history intracranial Ewing sarcoma including cerebral metastases

2.1.2.3 Patients with evidence of active bleeding, intratumoral hemorrhage or history of bleeding diatheses

2.1.2.4 Patients who are receiving anticoagulants other than prophylactic anticoagulation of venous or arterial access devices, provided that requirements for PT, PTT and fibrinogen are met, as described in Section [Error! Reference source not found.](#)

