The most profound toxicity seen was hemorrhage. The tendency for bleeding occurred infrequently and in early reports was attributed to thrombocytopenia and accounted for 3 deaths out of 84 patients treated (33). Subsequent studies showed that bleeding occurred early in treatment at about day 4 and was dose related occurring in 5.4% of 1150 patients treated at 30 mcg/kg/day or less (25). This time frame is significantly shorter than what is typically seen for chemotherapy induced thrombocytopenia. In addition, it appears as though the platelet count remained >20,000/mcL in most of the cases of hemorrhage in the literature. Subsequent to these studies, it was determined that mithramycin treatment caused a decrease in coagulation factors II, V, VII and X (34). In addition, subsequent studies revealed that mithramycin causes abnormal platelet adhesion in the setting of a normal platelet count consistent with a platelet adhesion

molecule deficiency (35). It is notable, that in addition to inhibiting EWS-FLI1, mithramycin is known to inhibit the SP1 transcription which is known to drive the biosynthesis of coagulation factors as well as platelet adhesion glycoproteins. Nevertheless, in all the cases of hemorrhage reported in the literature, it is not clear if the patients were taking any anti-coagulation medications, what type of blood product support was provided, and how effective the blood product support was in that era of treatment. In particular, it is not clear if patients received platelets in the setting of a normal platelet count as would be required for an acquired platelet adhesion defect. Regardless of the etiology, this side effect must be approached with extreme caution.

Another rare but significant side effect described in the literature is the report of toxic epidermal necrolysis that has been associated with mithramycin treatment (36, 37). This side effect is reported in two separate case reports but was omitted in the package insert from Pfizer (37) and appears to begin with plethora and non-specific skin findings. The incidence of this side effect is unclear, however due to the substantial nature of this reaction, all skin eruptions should be approached with significant caution.

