2.1.1.6 Recovered from acute toxicities of prior therapy to \leq Grade 1; specifically

a) Hematologic and Coagulation Parameters

- i. Peripheral ANC \geq 1000/mcL
- ii. Platelets \geq 75,000/ mcL (transfusion independent)
- iii. Hemoglobin \geq 8 g/dL (PRBC transfusions permitted)
- iv. Normal PT/PTT with the exception of a lupus anti-coagulant, which is permitted, may be corrected with Vitamin K administration or transfusion. Fibrinogen \geq the lower limit of normal.

b) Hepatic Function

- i. Bilirubin (total) \leq 1.5 X upper limit of normal (ULN)
- ii. ALT (SGPT) \leq 2.5 X ULN
- iii. Albumin $>$ 2 g/dL

c) Renal Function

- i. Creatinine clearance \geq 60 mL/min/1.73 m², or serum creatinine base on age and gender as follows:

Age (years)	Maximum Serum Creatinine (mg/dL)	
2 to $<$ 6	0.8	0.8
6 to $<$ 10	1	1

10 to < 13	1.2	1.2
13 to < 16	1.5	1.4
≥ 16	1.7	1.4

- Normal calcium, magnesium and phosphorus (can be on oral supplementation)

2.1.1.7 Cardiac Function: Left ventricular ejection fraction (EF) within normal institutional limits by Echocardiogram MUGA or cardiac MRI.

2.1.1.8 Ability to give informed consent. For patients <18 years of age their legal guardian must give informed consent. Pediatric patients will be included in age-appropriate discussion in order to obtain verbal assent.

2.1.1.9 Female and male patients (and when relevant their partners) must be willing to practice birth control (including abstinence) during and for two months after treatment, if of childbearing potential during sexual contact with a female of childbearing potential.

2.1.1.10 A durable power of attorney (DPA) will be offered to all patients ≥ 18 years old.

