2.1.2.5 Investigational Drugs: Patients who are currently receiving another investigational drug

2.1.2.6 Patients who are concurrently receiving agents, which may increase the risk for mithramycin related toxicities, such as hemorrhage including:

- Thrombolytic agents

- Anti-inflammatory drugs, nonsteroidal (NSAIDs) or aspirin or salicylate-containing products, which may increase risk of hemorrhage
- Dextran
- Dipyridamole
- Sulfinpyrazone
- Valproic acid

- 2.1.2.7 **Anti-cancer Agents:** Patients who are currently receiving other anti-cancer agents
- 2.1.2.8 Lactating or pregnant females (due to risk to fetus or newborn, and lack of testing for excretion in breast milk).
- 2.1.2.9 Patients with history of HIV, HBV or HCV due to potentially increased risk of mithramycin toxicity in this population.
- 2.1.2.10 Hypersensitivity to plicamycin (mithramycin)
- 2.1.2.11 Requirement for any of the contraindicated medications: nonsteroidal anti-inflammatory drugs, aspirin, dextran or other iron containing solutions (due to incompatibility), dipyridamole, sulfinpyrazone or valproic acid
- 2.1.2.12 Patients who in the opinion of the investigator may not be able to comply with the safety monitoring requirements of the study.
- 2.1.2.13 Patients receiving concurrently other therapies directed at their cancer.

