10.1.6 Contraindications

The following medications are contraindicated:

- Anticoagulants, coumarin- or indandione-derivatives
- Heparin other than heparin flushes
- Thrombolytic agents
- Anti-inflammatory drugs, nonsteroidal (NSAIDs) or aspirin or salicylate-containing products, which may increase risk of hemorrhage
- Dextran
- Dipyridamole
- Sulfapyrazone
- Valproic acid

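### The line-prophylaxis exception in 2.1.2.4 admits anticoagulants that 10.1.6 contraindicates with mithramycin

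*Combined protocol and SAP*

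**What the plan says.** Section 2.1.2.4 (exclusion criteria) bars "Patients who are receiving anticoagulants other than prophylactic anticoagulation of venous or arterial access devices", and attaches a laboratory condition to the exception: "provided that requirements for PT, PTT and fibrinogen are met". It does not limit the exception by agent, dose or route.

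The laboratory requirements are in 2.1.1.6: normal PT/PTT (lupus anticoagulant excepted) and fibrinogen no lower than the lower limit of normal. For PT/PTT, the same item adds that it "may be corrected with Vitamin K administration or transfusion".

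Section 10.1.6 lists what must not be given with mithramycin. Two of its entries are anticoagulants: "Anticoagulants, coumarin- or indandione-derivatives", with no exception, and "Heparin other than heparin flushes".

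Two other exclusions deal with medication. Section 2.1.2.6 covers "Patients who are concurrently receiving agents, which may increase the risk for mithramycin related toxicities, such as hemorrhage including", followed by a list. Section 2.1.2.11 begins "Requirement for any of the contraindicated medications: nonsteroidal anti-inflammatory drugs, aspirin, dextran" and continues with further named drugs.

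**The concern.** The two sections draw the line in different places. Section 2 turns on the purpose of the anticoagulant (protecting an access device); section 10 turns on the agent and, for heparin, on whether it is a flush. Where the purpose is allowed and the agent is not, staff who apply the eligibility section correctly can enroll a patient on a contraindicated drug. Nothing in section 2 requires the prophylaxis to be changed before entry.

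The stake is bleeding. Section 1.2.3 states: "The most profound toxicity seen was hemorrhage". It reports bleeding in 5.4% of 1150 patients treated at 30 mcg/kg/day or less, a fall in factors II, V, VII and X, and impaired platelet adhesion. It also says that the anticoagulant use of past patients who bled is unknown, so the historical record gives no reassurance about the combination.

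**Working it through.** There is no design figure to reproduce. The check sets the rules side by side and asks whether any other clause reconciles them.

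**Step 1. What each section allows**

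| Line prophylaxis | 2.1.2.4 (if PT, PTT and fibrinogen criteria are met) | 10.1.6 |
|---|---|---|
| Heparin flush | Not excluded | Allowed |
| Non-flush heparin | Not excluded | Contraindicated |
| Coumarin or indandione derivative | Not excluded | Contraindicated |

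The sections agree on the first row and disagree on the other two.

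**Step 2. Whether the medication exclusions close the gap**

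| Entry in 10.1.6 | Named in 2.1.2.6 | Named in 2.1.2.11 |
|---|---|---|
| Coumarin/indandione anticoagulants | No | No |
| Heparin other than flushes | No | No |
| Thrombolytics | Yes | No |
| NSAIDs, aspirin, salicylates | Yes | Yes |
| Dextran | Yes | Yes |
| Dipyridamole | Yes | Yes |
| Sulfinpyrazone | Yes | Yes |
| Valproic acid | Yes | Yes |
| Total of 8 | 6 | 5 |

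Every entry in 2.1.2.11 is also in 2.1.2.6, so the number named in neither is 8 − 6 = 2, and both are the anticoagulant entries. Two judgements enter the counts: 2.1.2.11 names NSAIDs and aspirin but not salicylate-containing products, and the spelling of sulfinpyrazone in 10.1.6 differs. Neither touches the anticoagulant rows.

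**Step 3. Whether the laboratory condition closes it**

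It narrows the group to patients whose PT, PTT and fibrinogen meet the criteria. It does not empty it. Prophylaxis that leaves PT/PTT normal passes directly. Where PT/PTT is abnormal, 2.1.1.6 allows the value to be corrected and does not ask for the anticoagulant to be stopped.

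**Step 4. Whether anything else does**

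Section 3.6 restricts only anticancer and investigational treatment. Section 4 says nothing on line prophylaxis.

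**Step 5. When 10.1.6 would take effect**

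Under 2.3.1, registration works from an eligibility checklist, and pharmacy is called once eligibility is confirmed. Appendix 7 places the baseline biopsy after enrollment and before treatment. The biopsy criteria in 2.1.1.11 test PT/PTT, platelets and ANC but contain no anticoagulant rule. A patient in the affected group could therefore have a research biopsy before a rule about co-administration with mithramycin comes into play.

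**The case against.** The strongest reply is that the rules do not strictly collide. An exclusion criterion says who may not enter; it does not instruct anyone to continue a drug. Section 10.1.6 binds every treated patient, and staff can satisfy both sections by switching the line to flushes before dosing. One can also read anticoagulation of an access device as meaning that the device, not the patient, is anticoagulated, which is a flush in all but name. The list in 2.1.2.6 is open-ended and could be taken to cover anticoagulants. Correcting the PT of a patient who stays on a coumarin is not a practice the protocol describes. Inpatient dosing in cycle 1, coagulation tests before and during each cycle, and the concomitant medication log make unnoticed co-administration less likely.

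Much of this limits the point without removing it. The flush-only reading is possible, but the text does not state it. Section 2.1.2.4 is the specific anticoagulant rule and carries an express exception, so the general wording of 2.1.2.6 does not clearly override it. The post-entry safeguards and 10.1.6 itself reduce the risk at dosing, but they do not amend eligibility and they come after enrollment and, for some patients, after the baseline biopsy. It stands that the subset is unquantified and may be empty, and that the stricter rule is already in the protocol.

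**Conclusion.** The inconsistency is real as written. Section 2.1.2.4 leaves eligible a group that 10.1.6 says must not receive mithramycin with their current medication: patients whose access-device prophylaxis is a coumarin, an indandione or non-flush heparin and who meet the PT, PTT and fibrinogen criteria.

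This is a safety-wording point, with no effect on the design's operating characteristics. It rests on one assumption about reading: that an exception with no limit on agent or route is applied as it stands, not as flushes only. The change should be made because the toxicity is serious and the remedy is cheap, but the point does not bear on the validity of the trial's results.

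**What to change.** In 2.1.2.4, limit the exception to heparin flushes of venous or arterial access devices, keeping the coagulation condition. In 2.1.2.11, add coumarin and indandione anticoagulants and heparin other than flushes, so that it agrees with 10.1.6 on these agents. If the sponsor does intend the wider exception, the alternative is to justify it and amend 10.1.6 to match.

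The cost is a wording amendment. Under the recommended version, a few patients may have to change line prophylaxis before entry or may not be enrolled.

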2.1.2.5 Investigational Drugs: Patients who are currently receiving another investigational drug

2.1.2.6 Patients who are concurrently receiving agents, which may increase the risk for mithramycin related toxicities, such as hemorrhage including:

- Thrombolytic agents

- Anti-inflammatory drugs, nonsteroidal (NSAIDs) or aspirin or salicylate-containing products, which may increase risk of hemorrhage
- Dextran
- Dipyridamole
- Sulfinpyrazone
- Valproic acid

- 2.1.2.7 **Anti-cancer Agents:** Patients who are currently receiving other anti-cancer agents
- 2.1.2.8 Lactating or pregnant females (due to risk to fetus or newborn, and lack of testing for excretion in breast milk).
- 2.1.2.9 Patients with history of HIV, HBV or HCV due to potentially increased risk of mithramycin toxicity in this population.
- 2.1.2.10 Hypersensitivity to plicamycin (mithramycin)
- 2.1.2.11 Requirement for any of the contraindicated medications: nonsteroidal anti-inflammatory drugs, aspirin, dextran or other iron containing solutions (due to incompatibility), dipyridamole, sulfinpyrazone or valproic acid
- 2.1.2.12 Patients who in the opinion of the investigator may not be able to comply with the safety monitoring requirements of the study.
- 2.1.2.13 Patients receiving concurrently other therapies directed at their cancer.

2.1.3 Recruitment Strategies

The following recruitment strategies will be employed to elicit potential candidates for this trial:

1. Listed on clinical trials.gov;
2. Listed in PDQ;
3. In addition, sarcoma patient advocacy and research groups such as the Children's Oncology Group, the Sarcoma Alliance for Research through Collaboration (SARC), The Sarcoma Foundation of America, The Liddy Shriver Sarcoma Initiative, the Quad W foundation will be notified.

Prior to distribution of any recruitment materials, such materials will be submitted to the NCI IRB for review.

2.2 SCREENING EVALUATION

2.2.1 General

Pre-treatment blood test should be performed within 7 days and imaging studies within 2 weeks prior to enrollment on the trial unless otherwise stated. The evaluations required prior to starting treatment are listed in table form in Appendix 3 Study Calendar.

HISTORY AND PHYSICAL EXAMINATION: including documentation of height and weight (average of 3 measurements on the same day), measurable disease, vital signs (blood pressure, heart rate, respiratory rate, temperature), performance status, history of bleeding disorder, HIV, HBV, HCV, and signs and symptoms within one week of enrollment.

2.2.2 Laboratory

2.2.2.1 ROUTINE LABS: complete blood count, differential, LDH, SGPT (ALT), SGOT (AST), alkaline phosphatase, bilirubin (total and direct), BUN, creatinine, amylase, lipase, electrolytes, calcium, magnesium, phosphorus, uric acid, albumin and thyroid panel.

2.2.2.2 Urinalysis.

2.2.2.3 URINE PREGNANCY TEST: required for females of childbearing potential

2.2.2.4 Coagulation Studies: PT/PTT/Thrombin Time/Fibrinogen, PFA-100, VWF antigen, VWF activity, Factor VIII activity, D-dimer, Fibrin degradation products and FXIII activity. In addition, 1 mL of plasma will be obtained, filtered through a 0.22 micron filter, frozen and saved for future clinical reference if needed ([Error! Reference source not found.](#) and [Error! Reference source not found.](#)).

2.2.3 Radiographic Evaluation

Assessment of disease sites by appropriate radiological evaluation. This could include a CT scan of chest, abdomen and pelvis and primary tumor, and bone scan, FDG-PET or MRI as indicated. A consistent method of disease evaluation for each patient will be used throughout the study.

Imaging of the head/brain to rule out intracranial disease including brain metastases is not required in all patients, but should be performed if there is clinical concern for intracranial disease/brain metastases

2.2.4 Cardiac Function Studies

Assessment of cardiac function (ejection fraction/shortening fraction) must be performed within 4 weeks of enrollment by MUGA or Echocardiogram to rule out cardiomyopathy. In addition, a 12-lead EKG must be performed.

2.2.5 Pathologic/Tissue Evaluation

Histologic confirmation of tumor will be performed on all patients by the NCI Laboratory of Clinical Pathology, NIH. For participants in the Phase II portion: the presence of the transcript with a CLIA approved EWS-FLI paraffin assay will be determined on samples from all sites in the Laboratory of Pathology CCR, NCI (See [Error! Reference source not found.](#)); unless a pathology report documenting presence of the transcript using a CLIA approved assay is obtained from the referring institution.

2.3.1 Registration at NCI

Authorized staff must register an eligible candidate with NCI Central Registration Office (CRO) within 24 hours of signing consent. A registration Eligibility Checklist from the web site (<http://home.ccr.cancer.gov/intra/eligibility/welcome.htm>) must be completed and faxed to [contact]. After confirmation of eligibility at Central Registration Office, CRO staff will call pharmacy to advise them of the acceptance of the patient on the protocol prior to the release of any investigational agents. Verification of Registration will be forwarded electronically via e-mail to the research team. A recorder is available during non-working hours.

3 STUDY IMPLEMENTATION

3.1 STUDY DESIGN

This study will be conducted as a single institution, open label Phase I/II trial of mithramycin. The Phase I portion will be conducted in children and adolescents (12 months to \leq 17 years of age) with refractory extracranial solid tumors. The cohort at the recommended dose or MTD will be expanded up to 12 patients, and attempts will be made to enroll at least 6 patients that are \geq 12 years of age and 6 patients that are $<$ 12 years of age to gain experience with a broad age range of patients.

In the phase II portion of the trial the adult dose (17.5 mcg/kg/dose) will be administered to patients with measurable refractory or recurrent Ewing sarcoma and EWS-FLI1 fusion transcript to determine the objective response rate (CR and PR) to mithramycin using RECIST criteria. Initially this portion of the trial will be open to eligible participants \geq 18 years of age. Enrollment will be expanded to include children and adolescents once safety at this dose is determined. If the pediatric phase II dose of mithramycin differs from the adult phase II dose, the protocol will be amended to address accrual and response rate to mithramycin in children in a separate stratum.

The Phase I and Phase II portions of the protocol will enroll patients simultaneously.

Patients with ESFT enrolled on this study (phase II portion) who meet eligibility criteria for tumor biopsies will undergo mandatory tumor biopsies to assess EWS-FLI1 target blockade by mithramycin (see [Appendix 7: Studies to be performed on tumor tissue](#)).

Mithramycin will be administered intravenously over 6 hours once daily for 7 days to be repeated every 28 days. Patients may continue to receive mithramycin for as long as they tolerate drug (Sections [3.1.1](#) and [3.4](#)) and do not have progressive disease (Section [6.2](#)).

Patients on study will be closely monitored for the development of toxicity including regular physical examinations, blood pressure monitoring, laboratory evaluations, and physical examinations with particular attention to the development of any signs of bleeding. Patients will be admitted to the hospital for the first treatment cycle during administration of mithramycin in order to allow for close monitoring of toxicities.

Disease will be monitored after every even treatment cycle using appropriate imaging studies using RECIST criteria.

Correlative studies are described in Section [5](#).

3.1.1 Dose Limiting Toxicity

Dose limiting toxicity (DLT) will be defined as non-hematologic toxicity and hematologic toxicity. Toxicities observed during the first treatment cycle will be used to determine the MTD. For the Phase II portion of the study, the below toxicities will be considered treatment limiting.

- **Non-hematologic DLT** will be defined as any grade ≥ 3 non-hematological toxicity possibly, probably, or definitely related to mithramycin with the exception of:
 - Grade 3 nausea that is controlled by symptomatic treatment with anti-emetics within 72 hours.
 - Grade 3 vomiting that is controlled by symptomatic treatment with anti-emetics within 72 hours.
 - Grade 3 diarrhea that is controlled by symptomatic treatment within 72 hours.
 - Asymptomatic grade 3 elevation of serum transaminases that return to \leq grade 1 within 14 days of completing mithramycin administration during a cycle.
 - Asymptomatic grade 3 electrolyte abnormalities that are correctable to grade 2 or less within 48 hours.
- **Hematologic DLT** will be defined as:
 - Grade 4 neutropenia (ANC $< 500/\text{mcL}$) on two consecutive blood counts drawn at least 72 hours apart in patients receiving prophylactic growth factor support (See Section 3.4) or
 - Grade 4 thrombocytopenia ($< 25,000/\text{mcL}$) refractory to platelet transfusion*.
 - Failure to recover platelet count to $\geq 75,000/\text{mcL}$ by day 42 of starting a treatment cycle.
- Any grade 2 bleeding not promptly (within 6 hours of appropriate intervention) corrected with blood product support will be considered dose-limiting.
- Bleeding that does not stop within 6 hours of administration of appropriate treatment including platelets, will be considered DLT and mithramycin will be discontinued.
- Any grade 2 mithramycin related toxicities of ≥ 7 days may be considered dose limiting if they are intolerable to the patient and cannot be controlled with standard supportive measures.
- Failure to recover from toxicity within 42 days of starting a treatment cycle to the level required for initiating subsequent cycles (Section 3.4) will be considered dose-limiting

*Thrombocytopenia will be allowed in this trial provided that that patient is not refractory to platelet transfusions and that the bone marrow recovers from the previous cycle. This toxicity will be tolerated because of the theoretical possibility that it reflects mithramycin inhibiting the target. It is known that FLI1 plays a prominent role in megakaryocyte development. Patients with haploinsufficiency of FLI1 are known to have congenital thrombocytopenia (Paris-Trousseau Syndrome) and megakaryocyte maturation arrest (44). Furthermore, mithramycin is believed to work by blocking binding of FLI1 since that portion of the EWS-FLI1 gene fusion protein is responsible for DNA binding. In addition, patients treated with mithramycin in the 1960s

experienced isolated thrombocytopenia. Therefore, it follows that if mithramycin blocks the action of EWS-FLI1, it may also affect FLI1 and therefore cause thrombocytopenia.

Details regarding the management of thrombocytopenia and bleeding are provided in Section: 4.1

Details regarding retreatment of patients experiencing neutropenia are provided in Section 3.3.

